## **8.9            HEALTH ECONOMICS**

Health Economics/Medical Resource Utilization and Health Economics parameters are not evaluated in this study.

## **8.10          TIMING OF STUDY ASSESSMENTS**

All assessments must be performed as per SoA (see Section [1.3](#)).

*As a rule, efficacy assessments supporting primary and secondary objectives ([Table 5](#)) are to be prioritized over exploratory assessments. As much as possible the sequence of assessments established for a given participant and their caregiver at the Baseline visit should be kept the same on the Day 183 and Day 365 visits. Specifically, for MSEL administration, all efforts should be made to perform the assessments at about the same time of day.*

*The timings of the qEEG blocks (first block starts 30 minutes before the morning meal and lasts until the start of this meal as specified in the SoA) should be recorded at about the same time of day at every visit.*

*Assessments listed in [Table 2](#) and [Table 4](#) of the SoA (see Section [1.3](#)) must be performed as specified at all indicated visits as these assessments will be important to confirm the PK model and to establish the exposure-qEEG relationship in Dup15q syndrome.*

*Caregiver-reported questionnaires can be completed either in the clinic or remotely within a 5-day window before the scheduled clinic visit, with remote support from the site as needed (see the SoA in Section [1.3](#)).*

*The Baseline, Day 183, Day 365 (Part 1) and Day 548, Day 730, Day 1095 (Part 2), Day 1125, and early termination (Part 2) visits can be split over 2 days if required to accommodate participants and families.*

### **8.10.1 Screening and Pre-treatment Assessments**

Written informed consent for participation in the study must be obtained before performing any study-specific screening tests or evaluations. ICFs for enrolled participant and for participants who are not subsequently enrolled will be maintained at the study site. Assent should be obtained for *participants* who, in the opinion of the investigator, are judged to be capable of giving assent.

All screening, and all pre-treatment assessments (related to entry criteria), must be completed and reviewed by the Investigator to confirm that participants meet all eligibility criteria. The Investigator will maintain a screening log to record details of all participants screened and to confirm eligibility or record reasons for screening failure.

The seizure diary and the wearable device should be handed out to the caregiver at screening to record baseline data as described in Section 8.2.4 and Section 8.1.5.12.

### **8.10.2 Assessments during Treatment**

Under no circumstances will participants who enroll in this study and complete treatment as specified be permitted to be allocated a new randomization number and re-enrolled in the study.

All assessments must be performed as per SoA (Section 1.3).

### **8.10.3 Assessments at Early Termination Visit**

Participants who discontinue from the study early will be asked to complete early termination assessments as per the SoA (Section 1.3) as soon as possible after the final dose of study treatment.

### **8.10.4 Follow-Up Assessments**

Participants who complete or who withdraw early from the study will be asked to attend a safety follow-up visit as described in the SoA (Section 1.3). For participants who consent to Part 2 OLE, the follow-up assessments will be completed at the end of Part 2 (see Section 4.1.1).

After the study completion/early termination visit, AEs should be followed as outlined in Sections 8.3.1 and 8.3.3.

## 9. **STATISTICAL CONSIDERATIONS**

### 9.1 **SAMPLE SIZE DETERMINATION**

Approximately 90 *participants* with *Dup15q* syndrome are planned to be randomized 2:1 to basmisanil or placebo. Assuming approximately 10% of randomized participants may not be evaluable for efficacy, there will be approximately 81 evaluable participants. The sample size may be increased in case of higher-than-expected rates of early study withdrawals or number of participants requiring dose adjustments due to exposures substantially deviating from target trough plasma concentrations.

The primary efficacy analysis will compare the change in Vineland-3 Adaptive Behavior Composite score from Baseline to Week 52 of treatment between the basmisanil and the placebo arm.

### 9.2 **SETS FOR ANALYSES**

For purposes of analysis, the following analysis sets are defined in [Table 13](#).

**Table 13 Analysis Sets**

Analysis Set	Description
Intent-to-treat (ITT)	All randomized participants who received at least one dose of study treatment. The ITT population will be the primary population for the analysis of all efficacy endpoints. Participants will be allocated to the treatment arm they were randomized to.
Safety	The safety analysis population equals the ITT population assuming treatment is received as assigned at randomization.
Pharmacokinetic (PK)	All participants who have received at least one dose of study treatment and who have data from at least one postdose sample will be included in the PK analysis population. Participants will be excluded from the PK analysis population if they significantly violate the inclusion or exclusion criteria, deviate significantly from the protocol, or if data are unavailable or incomplete which may influence the PK analysis. Excluded cases will be documented with the reason for exclusion. All decisions on exclusions from the analysis will be made prior to database closure.

If, at any time during *Part 1* of the study, participants receive treatment different from the one they were randomized to, manual re-assignments of participants to treatment arms

for the purpose of *the analysis of safety data* may be made depending *on* the duration of such incorrect treatment. Such re-assignments, if any, can only be made after unblinding and will be described in detail.

### **9.3 STATISTICAL ANALYSES OF PART 1**

#### **9.3.1 Demographics and Baseline Characteristics**

Demographic and baseline characteristics will be summarized by treatment group using means, standard deviations, medians, and ranges for continuous variables and proportions for categorical variables, as appropriate. Analyses will be performed in all randomized participants and in the intent-to-treat (ITT), if different.

Baseline will be defined as the latest available value prior to the first dose of study treatment.

#### **9.3.2 Efficacy Analyses**

The primary efficacy analysis will take place after all participants complete 52 weeks of *double-blind* treatment or *are* prematurely withdrawn.

A large black rectangular box covers the majority of the page below the text, indicating that the content has been redacted.

*In addition, results for the primary and secondary efficacy endpoints in Part 1 will be presented in descriptive summary tables and graphs, as appropriate. Listings will be prepared as required. Change from baseline for continuous endpoints will be analyzed using the same methodology as that for the primary endpoint. All statistical analysis methodologies will be described in detail and documented in the Sponsor's trial master file prior to performing any of the planned interim or final analyses.*

In addition to the primary analysis in the ITT, selected endpoints may be analyzed in subgroups, including by key demographic variables and stratification factors.

### **9.3.3 Safety Analyses**

All safety analyses will be based on the safety analysis population. Safety endpoints will be described in appropriate summary tables and graphs. Individual outputs will be presented if required.

Descriptive summaries of exposure to study treatment will be prepared by treatment group (including treatment duration, total dose received, dose intensity).

Verbatim AE terms recorded in the eCRF will be mapped to MedDRA thesaurus terms. AE severity will be graded according to National Cancer Institute Common Terminology Criteria for AEs (v5.0). Data on AEs, SAEs, and deaths will be presented by treatment group in summary tables and in individual outputs, as appropriate.

Abnormal changes in EEG recordings compared to baseline will be presented in summaries and individual outputs with a focus on treatment-emergent epileptiform abnormalities. Seizure status as derived from the seizure diary entries by caregivers will be used to analyze changes from baseline in seizure types, frequency, and duration.

All clinical laboratory data will be stored on the database in the units in which they were reported. Laboratory test values will be presented in International System of Units (Système International d'Unités [SI] units;). Individual outputs will show flags for abnormal results. Summaries and shift tables will be prepared for selected laboratory tests to describe baseline and maximum post baseline severity grade.

Vital sign data will be presented *by individual listings* with flagging of values outside the normal ranges and flagging of abnormalities.

ECG data as well as data for height, weight, and head circumference will be presented using appropriate summaries and/or listings.

Suicidality questions adapted from the C-CASA will be analyzed descriptively in *participants aged 6 years and above*.

Tanner staging over time will be described in *participants from age 9*.

**Concomitant Medications:** The original terms recorded on the participants' eCRF by the Investigator for concomitant medications will be standardized by the Sponsor by utilizing a mapped term and appropriate drug dictionary level. Concomitant medications will be presented using appropriate outputs.

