#### **4.1.3 Stopping Rules Criteria**

Dosing will be stopped at any time during the study in a given individual participant if one of the following circumstances occurs:

- A QTc using the Fridericia's correction factor (QTcF) value > 480 msec (when confirmed in repeat measurement within 30 minutes) or a QTcF change from baseline > 60 msec (when confirmed in repeat measurement within 30 minutes) for participants **older than 10 years old**;

OR

- A QTc using Bazett's formula (QTcB) value > 480 msec (when confirmed in repeat measurement within 30 minutes) or a QTcB change from baseline > 60 msec (when confirmed in repeat measurement within 30 minutes) for participants **up to, and including, the age of 10 years** (Bazett's correction is more appropriate in young children, see Section 8.2.6).
- Worsening of seizure frequency or occurrence of de novo seizures, which are considered clinically relevant in the opinion of the Investigator based on the following criteria:
  - persistent over time,
  - OR
  - notably deviate from the expected fluctuations in seizure status based on the participant's medical history,
  - OR
  - cannot be explained by the expected natural course of the disease,
  - OR
  - making the benefit-risk ratio non-favorable for the individual.

Other AEs that may lead to discontinuation of study treatment following evaluation on a case-by-case basis are described in Section 8.3.8. Before permanently discontinuing study treatment, an interruption should be considered, and study treatment may be restarted as detailed in Section 6.6.1. Unless it is determined by the Investigator that the occurrence is not related to the administration of study treatment, study treatment should not be restarted (see Section 7.1).

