#### **6.5 CONCOMITANT THERAPY**

Concomitant therapy includes any medication, e.g., prescription drugs, over-the-counter (OTC) drugs, vaccines (including COVID-19 vaccines), approved dietary and herbal supplements and nutritional supplements used by a participant from 6 weeks prior to

screening until the follow-up visit. *See also stability requirements for a ketogenic diet in Section 5.3.*

**Anti-epileptic medication** must be on a stable regimen 8 weeks prior to screening and for at least the first 4 weeks of treatment *in Part 1*. After the Day 28 visit, dose adjustments within the therapeutic range, and changes within the same class of anti-epileptic medication may be allowed as part of routine clinical care, upon consultation with the Medical Monitor. *In Part 2, for the first 28 days (until Day 395) dose changes are not allowed. Changes in the number or the class of anti-epileptic medications are not allowed until the Part 1 follow-up visit for participants who do not continue study participation in the optional OLE or until the Day 548 visit for participants who roll over to Part 2 of the study.*

The Medical Monitor should be contacted if there are any questions regarding concomitant or prior therapy.

All concomitant medications should be reported to the Investigator and recorded on the Concomitant Medications electronic Case Report Form (eCRF) along with reason for use, dates of administration (including start and end dates) and dosage information (including dose and frequency).

All medication administered to manage AEs should be recorded on the Adverse Event eCRF.

**Non-pharmacological** (e.g., physiotherapy) / **behavioral therapies** should not be stopped or newly started at least 6 weeks prior to screening and are expected to remain stable *until the Part 1 follow-up visit or until the Day 548 visit for Part 2 participants (excluding changes related to standard age and educational interventional programs or minor interruptions such as illness or vacation).*

Non-pharmacological / behavioral therapies should be reported on the *appropriate* eCRF page.

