#### Benzodiazepines / GABAergic medications

Benzodiazepines and benzodiazepine-related drugs may be exceptionally used with the following restrictions:

- **For the treatment of intermittent medical conditions** (e.g., for insomnia and anxiety / agitation, analgosedation)
  - Medications with a short half-life (e.g., lorazepam, alprazolam, or oxazepam) are preferred
  - Short-term use only (no more than 4 days per month)
  - Should not be taken within 2 days before a scheduled visit
- **For the treatment of emergency situations** (e.g., for the acute management of a seizure)
  - *If benzodiazepines/benzodiazepine-related drugs are required in an emergency situation, the visit can be rescheduled to allow for a 2-day window between emergency medication and visit date (even if it falls out of the protocol defined visit window).*
  - If benzodiazepines, in particular diazepam, midazolam, or clonazepam are used, the Investigator should be aware that a higher-than-normal dose of the medication may be required to achieve clinical response.
  - Similarly, in case of acute use of anesthetics that are GABAA positive allosteric modulators (e.g., volatile anesthetics or hypnotics) in a participant treated with

basmisanil, a higher dose of the anesthetics may be required to achieve the desired effect.

As described above, these recommendations are based on the potential for competition (PD interaction) at the GABAA receptor level.

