### **6.6.1 Temporary Interruption**

Before permanently discontinuing study treatment (regardless of whether initiated by the participant/*caregiver*, the Investigator or Sponsor), an interruption should be considered. Temporary study treatment interruption is an acceptable method to manage AEs related to the study treatment.

Participants who have temporarily interrupted should be considered for restarting study treatment as soon as medically justified in the opinion of the Investigator.

Study treatment should be interrupted if individual stopping rules are met (see Section 4.1.3) and to manage specific AEs and resumed as detailed in Section 8.3.8. Study treatment may be resumed with the joint agreement of the Investigator and the Sponsor's Medical Monitor when follow-up test results show that the participant no longer meets the dose interruption criteria. Unless it is determined by the Investigator that the occurrence is not related to the administration of the study treatment, study treatment should not be restarted.

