### **7.1 DISCONTINUATION OF STUDY TREATMENT**

For data to be collected at the time of treatment discontinuation and follow-up and for any further evaluations that need to be completed see the SoA (Section 1.3).

Reasons for discontinuation of study treatment may include, but are not limited to, the following:

- Any medical condition that the Investigator or Sponsor determines may jeopardize the participant's safety if he or she continues study treatment.
- Investigator or Sponsor determination that treatment discontinuation is in the best interest of the participant.
- Participant suicidal behavior or active suicidal ideation with specific plan and intent.

- An event that meets the stopping criteria (see Section 4.1.3).
- Pregnancy.
- Specific AEs if discontinuation of study treatment is required to manage the event (see Section 8.3.8).
- Symptomatic participants with moderate or severe COVID-19 infection (as per WHO guidelines) with signs of pneumonia or hypoxia.

Every effort should be made to obtain information on participants who discontinue study treatment but have not withdrawn consent. Participants who discontinue study treatment prematurely (*Part 1 or Part 2*) will be asked to return to the clinic for a study early termination visit (see Section 8.10.3) and *will be asked to complete the follow-up visit* (see Section 8.10.4), unless the participant withdrew consent. The primary reason for premature study treatment discontinuation should be documented on the appropriate eCRF.

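### Does the seizure-frequency analysis in Section 9.3.3 need stated rules for medication changes and treatment stops, and a composite worsening output?

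*Combined protocol and SAP*

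**What the plan says.** Table 5 lists change from baseline in diary-reported seizure frequency, duration and type as a secondary safety endpoint. The only analysis statement is in Section 9.3.3, where seizure status "derived from the seizure diary entries by caregivers will be used to analyze changes from baseline in seizure types, frequency, and duration", in the safety population.

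Section 8.2.4 describes seizure status as the investigator's determination at scheduled timepoints, made from caregiver report and the diary. It places the review period for each assessment in Table 11, which the public text does not reproduce. Table 1 schedules seizure status at Baseline, Days 28, 92, 183, 274 and 365, follow-up and early termination. The diary runs from screening to Day 365.

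Several actions can follow worsening:

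- Section 6.5 keeps anti-epileptic medication stable for the first 4 weeks of treatment. Then: "After the Day 28 visit, dose adjustments within the therapeutic range, and changes within the same class of anti-epileptic medication may be allowed". A limit remains: "Changes in the number or the class of anti-epileptic medications are not allowed until the Part 1 follow-up visit" for those who do not enter Part 2, and until Day 548 for those who do.
- Section 6.5.3 permits emergency benzodiazepines. The consequence given for assessments is a moved visit: "If benzodiazepines/benzodiazepine-related drugs are required in an emergency situation, the visit can be rescheduled".
- Section 4.1.3 includes among the reasons to stop dosing "Worsening of seizure frequency or occurrence of de novo seizures, which are considered clinically relevant in the opinion of the Investigator". Section 6.6.1 adds: "Study treatment should be interrupted if individual stopping rules are met".
- Under Section 7.1, participants who stop early "will be asked to return to the clinic for a study early termination visit" and are asked to complete the follow-up visit.

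Section 9.3.2 sends the full statistical methods to the trial master file, to be documented before any interim or final analysis.

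**The concern.** The endpoint can trigger the events that disturb its own measurement. A child whose seizures worsen is the one most likely to have an anti-epileptic dose raised, to receive an emergency benzodiazepine, or to have study treatment interrupted or stopped. If later diary counts are lower for those reasons, or if participants who stop drop out of the later summary, a real excess on basmisanil could look smaller than it was.

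Section 2.3.1.2 says that the risk of provoking or worsening seizures in this population has not been settled, and seizure frequency is the direct measure of it. Section 9.3.3 names no time window and no rule for data after these events. It also names no output that sets frequency beside medication changes and seizure-related stops by arm. A frequency table could therefore look milder than the adverse-event and discontinuation tables, with nothing planned to reconcile them.

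**Working it through.** **The plan's own figures.** No figure is stated for seizure frequency, so there is nothing on this endpoint to reproduce. The head count does reproduce: 90 × (1 − 0.10) = 81 evaluable for efficacy, and 2:1 allocation of 90 gives 60 and 30.

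**The window.** Section 9.3.3 analyzes seizure status. Section 8.2.4 ties seizure status to scheduled assessments and to review periods in Table 11. The window is thus assigned to a table that the public text lacks and cannot be counted as absent from the plan. What is open is which of those periods enters the change-from-baseline summary.

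**Time with fixed anti-epileptic medication.** 28/365 = 7.7% of Part 1. Dose and within-class changes are possible in the other 337/365 = 92.3%. The Day 28 seizure status comes before such changes are permitted.

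**Possible attenuation (all rates are assumptions).** Let w be the share of participants with epilepsy whose seizure rate doubles: 0.30 on basmisanil and 0.10 on placebo, a contrast of 0.200 in mean excess if nobody is up-titrated or stopped. Let u be the share of worsened participants up-titrated, s the share stopped, and r the share of the excess that up-titration removes.

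- A, late window, stoppers left out: w[(1 − u − s) + u(1 − r)]/(1 − ws)
- B, late window, stoppers' early-termination value kept: w(1 − ur)
- C, rate over own time on treatment, up-titration at about Day 92: w(1 − 0.75ur)

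| (u, s) | r | A | B | C |
|---|---|---|---|---|
| (0, 0) | any | 0.200 | 0.200 | 0.200 |
| (0.1, 0.1) | 0.5 | 0.177 | 0.190 | 0.1925 |
| (0.1, 0.1) | 1 | 0.167 | 0.180 | 0.185 |
| (0.3, 0.2) | 0.5 | 0.141 | 0.170 | 0.1775 |
| (0.3, 0.2) | 1 | 0.109 | 0.140 | 0.155 |

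Relative to 0.200, the loss at (0.1, 0.1) is 11% to 17% (A), 5% to 10% (B) and 4% to 8% (C). At (0.3, 0.2) it is 29% to 46%, 15% to 30% and 11% to 23%. The large losses need stoppers to be left out, which the plan does not say.

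**Direction.** The table applies the same u and s to both arms, so the contrast can only shrink. Under B with r = 1, take u = 0.1 on basmisanil and 0.5 on placebo: 0.30 × 0.9 − 0.10 × 0.5 = 0.27 − 0.05 = 0.22, which is larger than 0.20. On the ratio scale, suppose 20% or 40% of placebo participants escalate and their rate falls by 30%. A true rate ratio of 1.5 then appears as 1.5/0.94 = 1.60 or 1.5/0.88 = 1.70.

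**What a composite of first worsening would show.** With 60% having epilepsy (the background figure in Section 2.2.1), the arms hold 60 × 0.6 = 36 and 30 × 0.6 = 18.

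- 11/36 versus 2/18 is a difference of 19 points, Newcombe 95% interval -6 to 38.
- With 80% having epilepsy, 14/48 versus 2/24 is 21 points, 0 to 36.
- Among about 24 and 12 without epilepsy, zero de novo seizures leave exact upper limits 1 − 0.025^(1/n) of 14% and 26%.

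**Where worsening already appears.**

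- Section 8.3.6 makes de novo seizures and new seizure types events of special interest.
- Appendix 2 and Appendix 3 make a pre-existing condition that worsens reportable as an adverse event.
- Section 9.3.3 gives exposure and adverse events by treatment group, and concomitant-medication outputs. Section 9.6 adds discontinuations from treatment and study.
- Section 4.1.2.1 gives the IMC unblinded summaries by arm and asks the SOC to help interpret seizure changes.

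**The case for a change.** The strongest case for a change is that the gap sits in text that is not blacked out, and no other visible section fills it. Section 8.3.7 keeps non-serious seizures that match the child's history out of adverse-event reporting, so the diary carries much of the quantitative signal. After a stop, the plan shows an early-termination and a follow-up visit but no continued assessment to Week 52. An analysis of completers alone could then miss everything: if 20% of the basmisanil arm had a tripled rate and all of them stopped, the true mean ratio would be 0.8 + 0.2 × 3 = 1.40, while completers would show 1.00.

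The silence of Section 9.3.3 on these events is real, and attenuation is plausible. The rest carries less weight. The plan specifies no completers-only analysis: the safety population is everyone randomized and dosed, and seizure status is collected at early termination. The exemption in Section 8.3.7 covers seizures in line with history, not worsening. The contrast of 0.200 is also a chosen target, namely the effect had nobody been up-titrated or stopped. A summary of all collected data, whatever medication was changed, estimates the effect with permitted care included, which is a legitimate safety question.

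**Conclusion.** No change to the plan is needed. This is missing detail that analysts fill sensibly. The ordinary reading of Section 9.3.3 is to summarize all collected seizure-status data by arm and visit, with early-termination and follow-up values. That summary would be read beside the Day 28 visit and the planned medication, exposure, adverse-event and discontinuation outputs. The methods document promised in Section 9.3.2 is the natural place for that detail and may already hold it.

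The effect on the by-arm contrast is unknown and may be zero. In the illustration it runs from a 46% loss to a gain from 20 to 22 points. Every rate behind those figures is an assumption, as is the share with epilepsy, which could exceed 60% because Stage 1 enrolls only participants with epilepsy.

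A composite of first worsening is a choice on which statisticians would differ. It needs a diary threshold not yet set. It needs reasons for anti-epileptic dose changes and for treatment interruptions, and a baseline count of rescue use, none of which is clearly recorded. It mixes events of different severity. At about 36 versus 18 participants its interval includes zero even when worsening is nearly three times as frequent (30.6% versus 11.1%). The gain is too uncertain to require it.
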